3. STUDY DESIGN

LACI-3 will be an investigator-led, Phase III, prospective, randomised, controlled, 2x2 partial factorial, open label, blinded outcome trial performed in multiple UK hospital-based centres. LACI-3 is open to support international collaboration. The trial received Scientific Advice from the Medicines and Health Care Regulatory Agency assisted by NHS England Medicines Repurposing Programme at a meeting on 2nd July 2024. All MHRA guidance has been incorporated into the design of LACI-3.

Duration: The trial will last for 52 months with the treatment phase for each participant starting from within one day of randomisation until the end of trial follow-up at 18 months.

Participants meeting inclusion/exclusion criteria will be randomised at participating hospitals.

Participants will be randomised to start one of four treatments; ISMN only; cilostazol only; both ISMN and cilostazol; or neither ISMN nor cilostazol. Patients with contraindications to cilostazol can be randomised to ISMN versus no ISMN arms only; patients with contraindications to ISMN can be randomised to cilostazol versus no cilostazol arms only. The partial factorial design allows testing of both drugs when given alone and together. As in LACI-2, the doses will be escalated until participants are on their full dose by 1 month. If a patient encounters intolerable side effects at full dose, then they will be able to remain on the highest dose regime that they can tolerate and this dose will be recorded. The total duration of the trial drug administration will be 18 months. After the end of follow-up, the patients will reduce the tablets over about two weeks and then stop the trial medication. They will return any unused drug to their local community pharmacy or the hospital pharmacy if more convenient for destruction.

Drug supply: Trial drug will be dispensed by hospital pharmacies. The first drug supply will be given at the randomisation visit if allocated to the IMP. The IMP re-supply for the followup at 6 and 12 months will be posted to participants. Participants can collect the IMP resupply in person from the recruiting site.

Participants should continue their allocated treatment until the end of 18-month follow-up.

Discontinuing the allocated treatment by the participant's direct clinical care team due to the occurrence of an outcome event does not constitute withdrawal.

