6.3 DOSING REGIME

Patients will be supplied with trial drug in its usual (marketing) packaging unaltered. Patients will be issued with instructions reflecting the allocated dosing schedule which will instruct them what tablets they have to take initially and how to increase the dose. They will receive a phone call after 1 to 2 and 3 to 4 weeks as per schedule below to guide dose escalation. If a patient encounters intolerable side effects they will be asked to return to the highest previously tolerated dose and this will be recorded in the eCRF and hospital notes. They will be given clear instructions by phone or in person (depending on the stage of the trial).

Patients will also receive instruction on how they should decrease the dose of trial drug incrementally at the end of the study.

Table 1: Patients randomised to Isosorbide Mononitrate alone - either XL or non-XL preparations, example. If a slow release preparation is not available, then a non-slow release preparation may be used, but the dose should be given half in the morning (e.g. 08.00 am) and half in the evening (e.g. 18.00hrs)

ISMN XL Dosing Regime		ISMN non-XL Dosing Regime			
David	ISMN XL 25mg		Davi	ISMN non-XL 20mg	
Day	Morning	Evening	Day	Morning	Evening
1-5	25mg	nil	1-5	nil	20mg
6-10	50mg	nil	6-10	20mg	20mg
11-15	50mg	nil	11-15	20mg	20mg
16-20	50mg	nil	16-20	20mg	20mg
At end of study		At end of	fstudy		
Week	Morning	Evening	Week	Morning	Evening
79	25mg	Nil	79	20mg	Nil
80	Nil	Nil	80	Nil	Nil

Table 2: Patients randomised to cilostazol alone

Cilostazol Dosing Regime					
Devi	Cilostazol				
Day	Morning	Evening			
1-5	Nil	50mg			
6-10	50mg	50mg			
11-15	50mg	100mg			
16-20	100mg 100mg				
At end of s	At end of study				
Week	Morning Evening				
79	50mg	50mg			
80	Nil	Nil			

Table 3: Patients randomised to both Isosorbide Mononitrate and Cilostazol

ISMN XL/Cilostazol Dosing Regime						
-	Isosorbide Mononitrate XL 25mg		Cilostazol			
Day	Morning	Evening	Morning	Evening		
1-5	25mg	nil	Nil	Nil		
6-10	50mg	nil	Nil	Nil		
11-15	50mg	nil	Nil	50mg		
16- 20	50mg	nil	50mg	50mg		
21-25	50mg	nil	50mg	100mg		
26-30	50mg	nil	100mg	100mg		
At end of stu	At end of study					
Week	Morning	Evening	Morning	Evening		
79	25mg	Nil	50mg	50mg		
80	Nil	Nil	Nil	Nil		

ISMN non-XL/Cilostazol Dosing Regime					
Davi	Isosorbide Mononitrate 20mg		Cilostazol		
Day	Morning	Evening	Morning	Evening	
1-5	nil	20mg	Nil	Nil	
6-10	20mg	20mg	Nil	Nil	
11-15	20mg	20mg	Nil	50mg	
16- 20	20mg	20mg	50mg	50mg	

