6.8 SAFETY ASSESSMENTS

Safety assessments for the trial drug will occur at 2-weekly intervals in the first month after randomisation and six-monthly intervals thereafter during the 18 months duration of the trial.

The local hospital sites will ask participants by phone about the presence of symptoms that might be related to taking the trial drugs (e.g., headache, bleeding) during the first month after randomisation
The central blinded trial co-ordinators will continue to ask participants about the IMP symptoms as a part of the postal questionnaire at 6, 12 and 18-months follow-up visits.

The local hospital sites will phone-visit participants at 2-weekly intervals in the first month, and at 6, 12, and 18-month follow-up visits to ask about adherence to trial medication.

Investigators from the local hospital sites and central trial co-ordinators will record and report the outcome and safety events including SAEs, SARs and SUSARs between randomisation and the last follow-up visit at 18 months based on the information from the follow-up questionnaires as well as alerts from the hospital records. The safety reporting will include two weeks after the last dose of IMP is administrated.

The IMP symptoms, drug adherence, outcome, and safety events will be recorded in the eCRF. The SAEs, SARs and SUSARs will be reported to the sponsor.

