6.9 STUDY ASSESSMENTS

Study assessments (see Table 2) include the maximum of the six planned study visits.

The first study visit includes consent, baseline information collection and randomisation. After eligibility confirmation and obtaining the informed consent, investigators will collect the baseline medical history data required for randomisation. The randomisation visit can take place on the same day as the consent visit at the clinic, if all required tests for eligibility criteria and the baseline information are available.

Baseline information will include the confirmation of eligibility and informed consent details, demographic information such as date of birth, sex assigned at birth, ethnicity, years of full-time education ^{62, 63} and occupation.

The medical history will contain details of incident stroke, past medical history, vascular risk factors, concomitant medications and the characteristics of the lacunar stroke and SVD features (white matter hyperintensities/hypoattenuation, and/or lacunes) on brain imaging.

Baseline brain MR (preferred wherever possible) or CT: To identify the index stroke or exclude other causes of symptoms, and assess the burden of SVD – this is the clinical scan with MRI (T2, FLAIR, T1, T2* or SWI and diffusion imaging) or CT obtained soon after the presentation with stroke to diagnose the stroke. Brain imaging in eligible patients with lacunar ischaemic stroke may show either:

- a recent, relevant (in time and location) acute small subcortical (lacunar) infarct,

- or, if no visible acute lacunar infarct, there is no other competing pathology as a cause for stroke (e.g. no acute cortical infarct, no intra-cerebral haemorrhage, no stroke mimic such as tumour, or subdural haematoma)... Investigators will post scans to the LACI-3 Imaging office in Edinburgh for central reading in DICOM format or upload them online to the database according to the imaging acquisition guidance.

In participants whose lacunar stroke occurred more than six months previously, or in whom there have been further neurological symptoms, any brain MRI or CT imaging performed in the interval between the index lacunar stroke and recruitment should also be sent for central reading.

Cognitive baseline testing: Participants will be assessed at baseline using the Montreal Cognitive Assessment (MoCA), and the timed Trail Making Test B for processing speed/executive function, and for the concentration, the backwards spelling from the MMSE.

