Drugs symptoms: Will be assessed by site investigators after randomisation at 1-2 weeks and 3-4 weeks visits and by the blinded central team at 6, 12 and 18 months using a short simple validated questionnaire to assess for symptoms potentially related to trial tablets as part of safety monitoring, including headache, dizziness, palpitations, altered bowel habit, falls, bruising and bleeding, as in LACI-2. The participant will be asked whether any symptoms were severe enough to interfere with normal daily activities. Participants will also be able to report any other symptoms and describe them in detail.

Drug adherence: Will be assessed by site investigators at each follow-up visit by phone. Participants will be asked about adherence to medication using a very short structured question. These contacts will be timed around prescribing for the next batch of IMP.

Blood pressure: Will be collected by the site hospital teams as a part of the baseline visit. BP measurements, if available, will be collected by sites as a part of the site phone follow-up at each follow-up visit. Sites can use self-recorded BP by the participant using their own BP monitor or self-reported from routine GP or other hospital measure. The medication list including antihypertensive drugs will be collected at each visit by the hospital team as a part of the data collection on the continuing routine stroke prevention therapy.

Health economics: EQ-5D-5L, EQ-VAS will be collected at 6, 12 and 18 months and measures to assess health economic usage and impact of trial drug (contact with health care, place of residence, return to work, etc) will be collected centrally at 18 months.

Repeat Brain CT or MRI: any repeat scanning performed to assess a recurrent neurological event during the trial will be anonymised and sent to Edinburgh for central blinded adjudication.

Follow-up:

After randomisation, all participants will be followed up for outcome and safety events until the end of their follow-up at the 18 months visit.

The follow-up includes five visits. Participants will be followed up remotely by phone and post for 18 months by two teams: the local site and the central research team. Each time, a questionnaire will be completed by a participant by telephone or on paper or both to collect trial outcomes.

Local site:

- Contact at one-two and three-four weeks by phone to advise on dose escalation, check symptoms and drug adherence, BP, outcomes and safety.

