+/- 1	+/- 1 week				+/- 3 weeks			+/- 5 weeks					
Phone	one Pho	ne Phone	Post	Post	Phone	Phone	Post	Post	Phone	Phone	Post	Post	Phone
	1												
												٠	
•	• •	•				•				•			
		•				•				•			
			•				•						
•	•												
			٠				•						
										•			
•	• •			•				٠				•	
•	• •	•				•				•			
•	• •			•				•			•)	
										1			
				٠				•				٠	
					٠				٠				٠
•	• •			•				•			•)	
				٠				٠				٠	
					• • • •	• • • •	• • • • • • • • •		• •	• • • • • • • • • • • •	• • • • • • • • • • • • • • •	• • •	• •

^a Randomisation visit can take place on the same day as the consent visit at the clinic, if all required tests for eligibility criteria and the baseline information are available.

^b Participants will be followed up remotely by phone and post for 18 months by two teams: local site and the central research team.

^c End of Study Visit is a follow-up visit at 18 months.

^d Copy of the diagnostic scan (CT or MRI) will be sent for central reading.

⁶ Full blood count, urea and electrolytes and renal function will be obtained from the most recent sample since the time of the index stroke. ¹ Blood pressure collection is optional depending if a participant has access to the BP monitor or GP or hospital measure is available.

⁹ Dispensing in 3-monthly intervals is allowed. IMP re-supply to be sent to the participants home address.

^h Recurrent ischaemic stroke, TIA, major systemic or brain haemorrhage, fatal or non-fatal MI, death of any cause, dementia

¹ Modified Rankin Scale can be obtained from the relative/carer or the local site if a participant is unable to be contacted. ¹ Stroke Impact Scale (SIS), Telephone MOCA, Telephone Interview for Cognitive Status (TICS), concentration (from MMSE), Animal naming, ZUNG

* SAE - Serious Adverse Event; SAR - Serious Adverse Reaction, SUSAR - Suspected Unexpected Serious Adverse Reaction

¹EQ5D5L, EQ-VAS - quality of life questionnaires will be done at baseline and each follow-up visit. The NHS and social service use will be done at 18 months visit

^m Women of childbearing potential must have negative urine pregnancy testing on the day of randomisation. If applicable, the central team will send the urine pregnancy test with the central follow-up paper questionnaire.

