13.6 END OF STUDY

The end of study is defined as the last participant's last visit.

The Investigators and/or the trial steering committee and/or the Co-Sponsors have the right at any time to terminate the study for clinical or administrative reasons.

The end of the study will be reported to the REC, Regulatory Authority, R&D Office(s) and Co-Sponsors within 90 days, or 15 days if the study is terminated prematurely. The Investigators will inform participants of the premature study closure and ensure that the appropriate follow up is arranged for all participants involved. End of study notification will be reported to the Co-Sponsors via email to [contact].

In accordance with ACCORD SOP CR011, a Research Study Report will be provided to the Co-Sponsors ([contact]) and REC within 1 year of the end of the study.

Within one year of the end of trial, the Investigator will publish summary results on the publicly accessible database that the trial was registered with, on behalf of the Co-Sponsors.

The Investigator will submit a short confirmatory e-mail to the MHRA ([contact]) once the result-related information has been uploaded to the public registry. The subject line of the email notification must state:'End of trial: result-related information: EudraCT XXXX-XXXXXXXX and/or IRAS ID XXXXXXX'. The Co-Sponsor(s) will be copied in this e-mail ([contact]). It should be noted that you will not get an acknowledgment e-mail or letter from the MHRA.

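### The defined end of study comes before the last participants' final dose and before the protocol's own safety window closes, and no scheduled contact covers the end of that window

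*Protocol*

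**What the plan says.** Protocol section 13.6: "The end of study is defined as the last participant's last visit". A footnote to the study assessments table in section 6.9 fixes which visit that is: "End of Study Visit is a follow-up visit at 18 months". The same section counts visits so that nothing follows it. The assessments "include the maximum of the six planned study visits", and after randomisation "The follow-up includes five visits", the fifth being month 18. The case report form list in section 7.2 also stops at month 18.

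On treatment, section 3 says "Participants should continue their allocated treatment until the end of 18-month follow-up" and then "After the end of follow-up, the patients will reduce the tablets over about two weeks and then stop the trial medication". Section 6.3 adds "Patients will also receive instruction on how they should decrease the dose of trial drug incrementally at the end of the study", and its tables show a reduced dose in week 79 and none in week 80. Section 13.7, by contrast, does not foresee trial drug being taken beyond the end of follow-up.

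On safety, section 6.8 says "The safety reporting will include two weeks after the last dose of IMP is administrated". Section 7.2 gives the same limit for serious adverse events. The introduction to section 10 applies it to all adverse events and treats that point as the completion of active follow-up. The follow-up text in section 6.9 instead ends outcome and safety follow-up at the 18-month visit.

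**The concern.** The protocol gives two ends of safety follow-up (the 18-month visit, and the last dose plus two weeks) and an end-of-study date that matches only the earlier one. If drug is taken after the 18-month visit, the later one is the operative safety window, and the trial is declared over while the last participants may still be dosing and recording is still required.

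Two things are at stake and should be kept apart. The first is the formal date. Section 13.6 ties the end-of-study notification to it, and section 13.5 starts the record-retention period from it. It should not come before trial dosing and mandatory safety recording have finished. The second is ascertainment. The sponsor chose a window reaching past the last dose, but no scheduled step looks at its final part, for the last participant or for any other who stays on drug to month 18.

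**Working it through.** The protocol states no figure for this gap, so the check is timeline arithmetic from its own entries.

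**Inputs.** Visit at 18 months (section 6.9). Last dose at the end of week 79 (section 6.3 tables), or about two weeks after follow-up ends (section 3). Safety window of 14 days after the last dose (sections 6.8, 7.2, 10). 1300 participants recruited over about 30 months (section 4.1). Four treatment groups, three of them with drug (section 3).

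**Position of the visit.** 18 × 365.25 / 12 = 547.9 days; 547.9 / 7 = 78.3 weeks.

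**Gap after an on-time visit**

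| Reading | Last dose | Safety window closes |
|---|---|---|
| Section 6.3 tables | day 79 × 7 = 553, about 5 days after the visit | day 553 + 14 = 567, about 19 days after the visit |
| Section 3 text | about 14 days after the visit | about 14 + 14 = 28 days after the visit |

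On both readings the visit comes before the last dose and before the window closes.

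**Effect of visit timing.** Section 6.9 places the site call about three weeks before the time point. Measured from that call, the gap is 19 + 21 = 40 days to 28 + 21 = 49 days, although the central telephone call at month 18 also collects safety events. Going the other way, if the final contact is three weeks late and drug reduction still starts at month 18, the tables' window has closed about 2 days earlier (21 − 19), while the section 3 window has about 7 days left (28 − 21). If it is five weeks late, both windows have closed, about 16 and 7 days earlier. The visit-window row of the table is not legible in the text available, so which tolerance applies to month 18 is an assumption.

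**Reach of section 13.6 alone.** Assume even recruitment: 1300 / 30 = about 43 per month. In the last 28 days of visits that is about 40 people. If three quarters are on drug, about 30. With a mean overrun of about 14 days, 30 × 14 / 365.25 = about 1.2 participant-years.

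**Reach of the missing contact.** As a ceiling, 1300 × 3/4 = 975 participants on at least one drug.
- 975 × 19 / 365.25 = 51 participant-years.
- 975 × 28 / 365.25 = 75 participant-years.
- Against 975 × 1.5 = 1462 participant-years of planned treatment: 51 / 1462 = 3.5% to 75 / 1462 = 5.1%.
- If 15% were lost (the sample-size allowance in section 9.1, used only as an illustration): 829 participants, giving 43 to 64 participant-years.

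**The case against.** The strongest reply is that little of this comes from section 13.6. It sets one trial-wide date. For almost every participant the study is still open throughout drug reduction and the safety window, so amending 13.6 changes nothing for them. That stands, and it is why the two reaches are computed separately.

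Second, 51 to 75 participant-years is a ceiling. It assumes everyone allocated drug is alive, retained and still dosing at month 18. It also takes three quarters as treated, although participants with a contraindication to one drug are randomised only to the other drug or none, which lowers the treated share. That stands too.

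Third, a reader might infer that events in the gap are lost or may not be reported. The protocol does not support this. Section 6.8 uses hospital-record alerts, section 7.2 lists the site, the participant, the GP, carers and relatives as sources, section 10 asks participants to report symptoms, and section 10.8 has events followed to an outcome. Nothing in section 13.6 ends the reporting duty, and the 90 days allowed for end-of-study notification outlast the gap. What is missing is scheduled ascertainment and a consistent date.

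Fourth, a reader might take section 6.11 as ruling out any later contact. It excludes only long-term follow-up, and a two-week safety window is not that. The evidence for the gap is the absence of any later contact in the visit schedule and form list.

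Finally, the month-18 visit has several parts, and a late central call could cover some or all of the window. It could, but the protocol does not ensure it. If drug reduction starts only after the actual visit, as section 3 reads, lateness does not help.

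**Conclusion.** The contradiction holds. As written, and with an on-time 18-month visit, the study ends about 5 to 14 days before the last participant's final dose (if that participant is still on drug) and about 19 to 28 days before the stated safety window closes. Sections 6.9 (follow-up text) and 13.7 conflict with sections 3, 6.3, 6.8, 7.2 and 10 on the same point. The post-treatment pregnancy test in section 10.9, due four days after stopping drug, is a further procedure that can fall after the declared end, with no contact stated for collecting the result.

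The effect of the section 13.6 date is small: about 30 participants on drug and about one participant-year, assuming even recruitment and three quarters treated. The lack of a scheduled contact at the end of the window is the broader matter, bounded above by about 51 to 75 participant-years and lower after losses, discontinuations and single-drug randomisations. That larger figure should not be attributed to section 13.6.

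The 18-month primary endpoint, the sample size and the power are unaffected. No view is taken on the dosing or dose-reduction rule.

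**What to change.** - Reconcile sections 3, 6.3, 6.8, 6.9 (follow-up text and table footnote), 7.2, 10, 13.6 and 13.7, so that they give one account of when trial drug stops relative to the 18-month visit and one end of safety follow-up.
- In section 13.6, define the end of study as no earlier than the date on which the last participant completes the safety window that the protocol states.
- Have sites close each participant's safety record with a medical-record check at the end of that window, using the access they already have. The check is needed in addition to the new date, because changing the date alone does not give earlier participants any scheduled ascertainment.

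The cost is amendment wording, formal closure a few weeks later, and one brief record check per participant.

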13.7 CONTINUATION OF DRUG FOLLOWING THE END OF STUDY

It is not currently envisaged that the trial drug will be continued beyond the end of the trial follow-up.

13.8 INSURANCE AND INDEMNITY

The Co-Sponsors are responsible for ensuring proper provision has been made for insurance or indemnity to cover their liability and the liability of the Chief Investigator and staff.

The following arrangements are in place to fulfil the Co-Sponsors' responsibilities:

• The Protocol has been authored by the Chief Investigator and researchers employed by the University and collaborators. The University has insurance in place

(which includes no-fault compensation) for negligent harm caused by poor protocol design by the Chief Investigator and researchers employed by the University.

- Sites participating in the study will be liable for clinical negligence and other negligent harm to individuals taking part in the study and covered by the duty of care owed to them by the sites concerned. The Co-Sponsors require individual sites participating in the study to arrange for their own insurance or indemnity in respect of these liabilities. Sites which are part of the United Kingdom's National Health Service have the benefit of NHS Indemnity.
- Sites out with the United Kingdom will be responsible for arranging their own indemnity or insurance for their participation in the study, as well as for compliance with local law applicable to their participation in the study.
- The manufacturer supplying IMP has accepted limited liability related to the manufacturing and original packaging of the study drug and to the losses, damages, claims or liabilities incurred by study participants based on known or unknown Adverse Events which arise out of the manufacturing and original packaging of the study drug, but not where there is any modification to the study drug (including without limitation re-packaging and blinding).

